8.4 Interim Safety Analysis

We have generated stopping rules based on the three year historical data from the JTCC for 5 criteria: NRM, Relapse, Graft Failure or Delay, Drug Intolerance, and Grade III-IV GVHD. These rules and the operating characteristics for the algorithms are presented below.

Stopping rules

In this section, the stopping rules for each of the adverse events non-relapse mortality, relapse, graft failure, intolerance to Telmisartan and Grade 3 or 4 GVHD by day 100 are described. Each of the 5 toxicities is monitored at 1% Type I error, i.e., the probability of stopping by chance the trial when in fact the toxicity rate observed in historical data is true. Thus, the repeated significance test maintains the level of the toxicity through all the monitoring points to be 1%.

Further, jointly all 5 toxicities have probability $(1-(1-0.01)^5)=0.049$ probability of stopping the trial by chance when the null hypotheses are true.

Non-Relapse Mortality (NRM) at 100 days

If the non-relapse mortality in patients receiving Telmisartan the rate of NRM exceeds 22% then the study will be stopped. The operating characteristics of the stopping rule are described below. Based on historical data from the cancer center registry, it was assumed that 15% incidence of NRM was considered expected and incidence greater than 22% would be considered unacceptable.

Using repeated significance testing (Jennison and Turnbull) with 15.0% as lower proportion and 22.0% as higher proportion, 1% alpha level, and 80% power for early termination, shape parameter of the boundary, $\delta=0.2$, with priority on alternative hypothesis and continuous monitoring, the following stopping guidelines were computed by the *toxbdry* function in the Clinfun package in R 3.2.0.

Table 5. Stopping Boundaries for NRM at 100 days using continuous monitoring

Monitoring Look	Number of Patients at Monitoring Look	Stop if Number of Toxicities is at least
1	2	2
2	7	3
3	12	4
4	18	5
5	24	6
6	29	7
7	35	8
8	41	9
9	47	10
10	54	11
11	60	12

The trial will be terminated if 2 patients out of the first 2 patients receiving experimental drug, Telmisartan, experience NRM by day 100. If out of the first 7 patients, 3 or more have NRM by day 100 then trial will be stopped. The boundaries were obtained such the Type I error, fixed at 1%, was spent over the multiple looks, hence the probability of stopping the trial prematurely by chance is 0.01.

Table 6. Operating characteristics for the stopping boundaries for NRM Day 100

Probability Of Toxicity	Probability of crossing low bndry	Probability of stopping low bndry	Expected sample size low bndry	Probability of crossing high bndry	Probability of stopping high bndry	Expected sample size high bndry
0.15	0.343	0.338	47.4	0.340	0.335	47.5
0.164	0.443	0.436	44.0	0.440	0.433	44.0
0.178	0.544	0.536	40.4	0.541	0.533	40.4
0.192	0.640	0.631	36.7	0.638	0.629	36.7
0.206	0.727	0.718	33.1	0.725	0.715	33.1
0.220	0.800	0.792	29.7	0.798	0.790	29.7

Bndry, boundary.

From the operating characteristics, the probability of stopping the trial due to NRM if the level of toxicity is at high level of 22% is 0.79. The expected sample size at termination of the trial is 29.7, if Telmisartan in fact more toxic than standard treatment.

Relapse at Day 100

If the incidence of relapse by day 100 in patients receiving Telmisartan exceeds 19% then the study will be stopped. The operating characteristics of the stopping rule are described below. Based on historical data from the cancer center registry, it was assumed that 12% incidence of relapse was considered expected and incidence greater than 19% would be considered unacceptable.

Using repeated significance testing (Jennison and Turnbull) with 12.0% as lower proportion and 19.0% as higher proportion, 1% alpha level, with priority given to the alternative hypothesis and 80% power to for early termination, shape parameter of the boundary, $\delta=0.2$, for continuous monitoring, the following stopping guidelines were computed by the *toxbdry* function in the Clinfun package in R 3.2.0.

Table 7. Stopping Boundaries for Relapse at Day 100

Monitoring Look	Number of Patients at Monitoring Look	Stop if Number of Toxicities is at least
1	3	2
2	8	3
3	15	4
4	22	5
5	29	6
6	37	7
7	44	8
8	51	9
9	59	10
10	60	11

For this continuous monitoring scheme, the trial will be terminated if 2 or more patients out of the first 3 patients receiving experimental drug, Telmisartan, experience relapse by day 100. If out of the first 8 patients, 3 or more have relapse by day 100 then trial will be stopped, and so forth. Out of all the 15 patients that receive Telmisartan, if 4 or more patients have relapse by day 100 then the drug will be considered more toxic than standard treatment. The boundaries were obtained such the Type I error, fixed at 1%, was spent over the multiple looks, hence the probability of stopping the trial prematurely by chance is 0.01.

Table 8. Operating characteristics for the stopping boundaries for Relapse by Day 100

Probability Of Toxicity	Probability of crossing low bndry	Probability of stopping low bndry	Expected sample size low bndry	Probability of crossing high bndry	Probability of stopping high bndry	Expected sample size high bndry
0.120	0.312	0.312	48.4	0.307	0.307	48.8
0.134	0.418	0.418	44.8	0.414	0.414	45.2
0.148	0.527	0.527	40.8	0.523	0.523	41.3
0.162	0.631	0.631	36.9	0.628	0.628	37.3
0.176	0.724	0.724	33.0	0.721	0.721	33.4
0.19	0.801	0.801	29.4	0.799	0.799	29.8

Bndry, boundary.

From the operating characteristics, the probability of stopping the trial due to grade 3 or 4 GVHD if the level of toxicity is at high level of 36% is 0.79. The expected sample size at termination of the trial is 31.8, if Telmisartan in fact more toxic than standard treatment.

Graft Failure at Day 100 (includes delayed engraftment and failure)

If the incidence of graft failure by day 100 in patients receiving Telmisartan exceeds 7.0% then the study will be stopped. The operating characteristics of the stopping rule are described below. Based on historical data from the cancer center registry, it was assumed that 7.0% incidence of relapse was considered expected and incidence greater than 12.0% would be considered unacceptable.

Using repeated significance testing (Jennison and Turnbull) with 7.0% as lower proportion and 12.0% as higher proportion, 1% alpha level, and 80% power to for early termination, shape parameter of the boundary, $\delta=0.2$, giving priority to the alternative hypothesis, and continuous monitoring the following stopping guidelines were computed by the *toxbdry* function in the Clinfun package in R 3.2.0.

Table 9. Stopping Boundaries for Graft Failure at Day 100

Monitoring Look	Number of Patients at Monitoring Look	Stop if Number of Toxicities is at least
1	9	2
2	21	3
3	33	4
4	45	5
5	58	6
6	60	7

The trial will be terminated if 2 or more patients out of the first 9 patients receiving experimental drug, Telmisartan, experience graft failure by day 100. If out of the first 21 patients, 3 or more have graft failure by day 100 then trial will be stopped. The boundaries were obtained such the Type I error, fixed at 1%, was spent over the multiple looks, hence the probability of stopping the trial prematurely by chance is 0.01.

Table 10. Operating characteristics for the stopping boundaries for Graft Failure Day 100

Probability Of Toxicity	Probability of crossing low bndry	Probability of stopping low bndry	Expected sample size low bndry	Probability of crossing high bndry	Probability of stopping high bndry	Expected sample size high bndry
0.07	0.373	0.373	46.1	0.365	0.365	46.2
0.08	0.477	0.477	42.4	0.467	0.466	42.5
0.09	0.576	0.576	38.7	0.565	0.565	38.8
0.10	0.666	0.666	35.0	0.655	0.654	35.1
0.11	0.744	0.744	31.6	0.734	0.733	31.7
0.12	0.809	0.809	28.5	0.799	0.798	28.6

Bndry, boundary.

From the operating characteristics, the probability of stopping the trial due to graft failure if the level of toxicity is at high level of 12% is 0.798. The expected sample size at termination of the trial is 28.6, if Telmisartan in fact more toxic than standard treatment.

Telmisartan Intolerance (includes angioedema and grade 3 or greater drug related adverse events after dose adjustments)

We use 5% as our acceptable rate of intolerance for drug treatment. Using repeated significance testing (Jennison and Turnbull) with 5.0% as lower proportion and 11.0% as higher proportion, 1% alpha level, and 80% power to for early termination, shape parameter of the boundary, delta=0.2, giving priority to the alternative hypothesis and continuous monitoring, the following stopping guidelines were computed by the *toxbdry* function in the Clinfun package in R 3.2.0.

Table 11. Stopping Boundaries for Intolerance to Telmisartan at Day 100

Monitoring Look	Number of Patients at Monitoring Look	Stop if Number of Toxicities is at least
1	8	2
2	22	3
3	38	4
4	55	5
5	60	6

The trial will be terminated if 2 or more patients out of the first 8 patients receiving experimental drug, Telmisartan, experience intolerance by day 100. If out of the first 22 patients, 3 or more have intolerance by day 100 then trial will be stopped. The boundaries were obtained such the Type I error, fixed at 1%, was spent over the multiple looks, hence the probability of stopping the trial prematurely by chance is 0.01.

Table 12. Operating characteristics for the stopping boundaries for Intolerance Day 100

Probability Of Toxicity	Probability of crossing low bndry	Probability of stopping low bndry	Expected sample size low bndry	Probability of crossing high bndry	Probability of stopping high bndry	Expected sample size high bndry
0.050	0.222	0.221	52.3	0.219	0.218	52.4
0.062	0.350	0.350	48.1	0.346	0.345	48.2
0.074	0.483	0.483	43.5	0.480	0.477	43.6
0.086	0.608	0.608	38.9	0.604	0.601	39.0
0.098	0.714	0.711	34.4	0.712	0.708	34.6
0.11	0.800	0.797	30.4	0.798	0.794	30.6

From the operating characteristics, the probability of stopping the trial due to intolerance if the level of toxicity is at high level of 11% is 0.794. The expected sample size at termination of the trial is 30.6, if Telmisartan in fact more toxic than standard treatment.

Grade 3 or 4 GVHD at 100 days

If the Grade 3 or 4 GVHD in patients receiving Telmisartan the rate of NRM exceeds 36% then the study will be stopped. The operating characteristics of the stopping rule are described below. Based on historical data from the cancer center registry, it was assumed that 26% incidence of NRM was considered expected and incidence greater than 36% would be considered unacceptable.

Using repeated significance testing (Jennison and Turnbull) with 26.0% as lower proportion and 36.0% as higher proportion, 1% alpha level, and 80% power for early termination, shape parameter of the boundary, $\delta=0.2$, with priority on alternative hypothesis and continuous monitoring, the following stopping guidelines were computed by the *toxbdry* function in the Clinfun package in R 3.2.0.

Table 13. Stopping Boundaries for NRM at 100 days using continuous monitoring

Monitoring Look	Number of Patients at Monitoring Look	Stop if Number of Toxicities is at least
1	3	3
2	5	4
3	8	5
4	11	6
5	14	7
6	18	8
7	21	9
8	24	10
9	28	11
10	31	12
11	35	13
12	38	14
13	42	15
15	45	16
16	49	17
17	52	18

18	56	19
19	59	20
20	60	21

The trial will be terminated if 3 patients out of the first 3 patients receiving experimental drug, Telmisartan, experience Grade 3 or 4 GVHD by day 100. If out of the first 5 patients, 4 or more have NRM by day 100 then trial will be stopped. The boundaries were obtained such the Type I error, fixed at 1%, was spent over the multiple looks, hence the probability of stopping the trial prematurely by chance is 0.01.

Table 14. Operating characteristics for the stopping boundaries for NRM Day 100

Probability Of Toxicity	Probability of crossing low bndry	Probability of stopping low bndry	Expected sample size low bndry	Probability of crossing high bndry	Probability of stopping high bndry	Expected sample size high bndry
0.26	0.253	0.247	51.5	0.247	0.247	51.5
0.28	0.359	0.351	48.1	0.351	0.351	48.1
0.30	0.478	0.467	44.3	0.467	0.467	44.3
0.32	0.597	0.695	40.2	0.585	0.585	35.2
0.34	0.708	0.695	35.9	0.695	0.695	35.9
0.36	0.801	0.790	31.8	0.790	0.790	31.8

Bndry, boundary.

From the operating characteristics, the probability of stopping the trial due to grade 3 or 4 GVHD if the level of toxicity is at high level of 36% is 0.79. The expected sample size at termination of the trial is 31.8, if Telmisartan in fact more toxic than standard treatment.

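### The five safety stopping rules are said to carry 1% type I error each (4.9% jointly), but the plan's own tables show 22–37% each, which is about 83% jointly under the plan's independence formula

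*Combined protocol and SAP*

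**What the plan says.** The opening of the stopping-rules text in section 8.4 states: "Each of the 5 toxicities is monitored at 1% Type I error". It defines this error as the chance of a stop "when in fact the toxicity rate observed in historical data is true". It then combines the five rules as 1 − (1 − 0.01)^5 = 0.049 and presents this as the joint "probability of stopping the trial by chance when the null hypotheses are true". After each of the five boundary tables (Tables 5, 7, 9, 11 and 13) the text repeats the claim: "hence the probability of stopping the trial prematurely by chance is 0.01".

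The design settings for non-relapse mortality (NRM) are "with 15.0% as lower proportion and 22.0% as higher proportion", with "1% alpha level, and 80% power for early termination, shape parameter of the boundary, $\delta=0.2$, with priority on alternative hypothesis and continuous monitoring". The other four rules use the same alpha, power, shape parameter and priority.

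Tables 6, 8, 10, 12 and 14 give the operating characteristics. The first row of each is the expected (null) rate. The prose discusses only the row for the unacceptable rate, where the stopping probability is about 0.80.

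**The concern.** The first row of each operating-characteristics table answers the same question as the 1% statement: how often does this rule stop the trial when the true rate is the expected one? The tables answer 22% to 37%, and the prose answers 1%. Both cannot describe the same boundaries.

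The rules are written as binding, and the DSMB and IRB use these figures to judge them. A reader of the prose would take a false stop for a 1-in-20 event and would read a crossing as strong evidence of harm. On the tabulated values a crossing is the more likely outcome for a drug no worse than history. The efficacy power in section 8.3.1 (85.8% for a true grade III–IV rate of 10%; 80.5% for a grade II rate of 57%) is computed for 60 patients and makes no allowance for stopping.

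**Working it through.** **Inputs.** Boundaries are from Tables 5, 7, 9, 11 and 13. Expected rates p0 and unacceptable rates p1 are from the text of section 8.4. The maximum is 60 patients.

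**Step 1: the plan's joint figure.** 1 − (1 − 0.01)^5 = 0.0490. The arithmetic is right; the question is the input of 0.01.

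**Step 2: the plan's tables.** I carried the binomial distribution of the event count forward one patient at a time, removing the probability that reaches the boundary at each step, under continuous monitoring to n = 60.

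| Rule | p0 / p1 | Tabulated crossing at p0 (low / high boundary) | Recomputed at p0 | Recomputed at p1 | Expected N at p0 / p1 |
|---|---|---|---|---|---|
| NRM | 0.15 / 0.22 | 0.343 / 0.340 | 0.341 | 0.798 | 47.5 / 29.7 |
| Relapse | 0.12 / 0.19 | 0.312 / 0.307 | 0.307 | 0.799 | 48.8 / 29.8 |
| Graft failure | 0.07 / 0.12 | 0.373 / 0.365 | 0.365 | 0.799 | 46.2 / 28.6 |
| Intolerance | 0.05 / 0.11 | 0.222 / 0.219 | 0.219 | 0.798 | 52.4 / 30.6 |
| Grade III–IV GVHD | 0.26 / 0.36 | 0.253 / 0.247 | 0.247 | 0.790 | 51.5 / 31.8 |

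The recomputed values match the high-boundary columns, including the expected sample sizes. The tables are therefore correct for the printed boundaries.

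**Step 3: does any reading give 1%?**
- Checking only at the listed looks leaves every crossing probability unchanged.
- Counting only stops before patient 60 changes NRM to 0.335 and the others by no more than about 0.001.
- The first look alone exceeds 1% for every rule. NRM, 2 of 2: 0.15² = 0.0225. Relapse, at least 2 of 3: 0.040. Graft failure, at least 2 of 9: 0.127. Intolerance, at least 2 of 8: 0.057. GVHD, 3 of 3: 0.26³ = 0.0176.

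**Step 4: why alpha was lost.** A single look at 60 patients with alpha at or below 0.01 has these thresholds and power at p1:

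| Rule | Stop if at least | Alpha | Power at p1 |
|---|---|---|---|
| NRM | 17 | 0.0059 | 0.15 |
| Relapse | 15 | 0.0041 | 0.15 |
| Graft failure | 10 | 0.0084 | 0.18 |
| Intolerance | 8 | 0.0098 | 0.34 |
| GVHD | 25 | 0.0059 | 0.22 |

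With 60 patients and these rate pairs, 1% alpha and 80% power are far from compatible. Giving priority to the alternative kept the power and released the alpha.

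**Step 5: joint false-stop probability.** The plan's own formula with the recomputed values gives 1 − (0.6592 × 0.6931 × 0.6348 × 0.7808 × 0.7525) = 1 − 0.1704 = 0.830. The four tabulated column sets give 0.828 to 0.835.

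The documents do not give the dependence between endpoints. Assuming a common latent within-patient correlation of 0.3, 0.5, 0.7 or 0.9 (20,000 simulated trials each), the joint figure is about 0.78, 0.73, 0.68 or 0.61. An assumed mixed-sign structure (NRM negatively related to relapse and positively to GVHD) gives about 0.82. The floor is the largest single rule, 0.365.

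**Step 6: effect on the efficacy question.** Suppose telmisartan lowers grade III–IV GVHD to 10% and the other four rates equal their expected values, independently.
- Probability that none of the other four rules crosses: 0.6592 × 0.6931 × 0.6348 × 0.7808 = 0.2265.
- The GVHD rule crosses with probability 0.002, so P(stopped) = 1 − 0.2265 × 0.998 = 0.774.
- P(no GVHD crossing and at most 8 cases in 60) = 0.858, so P(reaching 60 with at most 8 cases) = 0.2265 × 0.858 = 0.194, against the stated power of 0.858.
- If NRM also falls, to 12%, 10%, 8% or 5% (assumed), P(stopped) is 0.71, 0.69, 0.67 or 0.66, and P(reaching 60 with at most 8 cases) is 0.25, 0.27, 0.28 or 0.29.

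**The case against.** The strongest defence is that the boundaries are correctly computed and may be a deliberate safety-first choice. The section says openly that priority went to the alternative, and the null rows are printed. That is fair to the boundaries, and nothing here says they are wrong. It does not rescue the prose, which asserts 0.01 beside tables showing 0.22 to 0.37 and never mentions the null rows. Readers are given two contradictory answers.

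Three qualifications stand.

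- The 0.83 is not printed in the plan. It is the plan's independence formula applied to the plan's tabulated values, and independence is doubtful: NRM excludes patients with recurrent cancer and includes fatal GVHD. The joint figure is best read as roughly 0.6 to 0.83.
- The 0.77 and 0.19 in Step 6 hold NRM at 15% while GVHD falls, although the plan regards intestinal GVHD as the main cause of early death. The range with lower NRM is the fairer summary. It remains far from 0.858.
- The recursion treats each day-100 outcome as known before the next patient enrols. Section 8.4 gives neither an accrual rate nor a pause while outcomes mature, so a crossing may be recognised after more patients have entered. Under independence the cumulative chance of a crossing is 0.67 by patient 30, 0.74 by patient 40 and 0.79 by patient 50. A trial that stops late would still leave useful data, so it is too strong to say that it could not answer its question at all.

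**Conclusion.** The concern holds. The 1% per-rule and 4.9% joint statements are false for the boundaries the trial will use. The per-rule error is 22 to 37 times the stated value. This can be read from the plan's own tables, is confirmed by exact calculation, and needs no assumption beyond independent patients with a constant event rate.

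The joint figure is 0.83 under the plan's independence assumption, 0.61 to 0.78 under the common positive correlations tried, and at least 0.365 whatever the dependence. Even that floor is more than seven times 0.049. A crossing is more likely than not under every dependence assumption tried, and the stated efficacy power substantially overstates the chance of completing 60 patients with a positive grade III–IV result. This must be corrected, because the DSMB relies on these error rates.

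**What to change.** **Minimum correction (wording only).** In section 8.4, delete every 1%, 0.01 and 0.049 statement, including the sentence repeated after each boundary table. State the actual false-stop probabilities of the printed boundaries (0.34, 0.31, 0.37, 0.22 and 0.25) and a joint figure of about 0.8, with its independence assumption and the range under dependence. In section 8.3.1, add the probability of completing 60 patients beside the efficacy power. This keeps all boundaries and resolves the contradiction.

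**Alternative (redesign).** Regenerate the boundaries with priority on the null so that 1% per rule is met, and state the resulting detection probabilities. With a reconstructed boundary of the same shape these are about 0.18, 0.21, 0.17, 0.31 and 0.25 at the unacceptable rates (a second reconstruction agreed to within 0.01), against about 0.80 now. The actual software output should replace them. That loss must be shown openly; the choice is for the sponsor and DSMB.

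**Same edit.** Reconcile the graft-failure text, which says the study stops above 7.0% but calls rates above 12.0% unacceptable. Replace the sentence after Table 8, which reports the GVHD results (36%, 0.79, 31.8) under relapse. Check the 0.32 row of Table 14, where a stopping probability of 0.695 exceeds its crossing probability of 0.597.

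**Cost.** A protocol amendment and DSMB notification, plus one software rerun if the redesign is chosen. No extra patients are needed. The stated figures become less favourable.

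### Section 8.4 gives two unreconciled stop instructions each for NRM, relapse and grade III-IV GVHD: a percentage sentence and a count table that disagree if the percentage is read as an observed rate

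*Combined protocol and SAP*

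**What the plan says.** For each of three criteria, section 8.4 (Interim Safety Analysis) gives a percentage sentence and then a table of counts.

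- **NRM at 100 days.** The sentence is "If the non-relapse mortality in patients receiving Telmisartan the rate of NRM exceeds 22% then the study will be stopped". The boundaries are then computed "with 15.0% as lower proportion and 22.0% as higher proportion, 1% alpha level, and 80% power for early termination". Table 5 lists the counts, and the text below it restates them as instructions: "If out of the first 7 patients, 3 or more have NRM by day 100 then trial will be stopped".
- **Relapse at day 100.** The sentence is "If the incidence of relapse by day 100 in patients receiving Telmisartan exceeds 19% then the study will be stopped". The design is "with 12.0% as lower proportion and 19.0% as higher proportion, 1% alpha level". The text under Table 7 says "If out of the first 8 patients, 3 or more have relapse by day 100 then trial will be stopped".
- **Grade 3 or 4 GVHD at 100 days.** The sentence ends "the rate of NRM exceeds 36% then the study will be stopped". It names NRM, but its place in the GVHD subsection and the 36% figure show that GVHD is meant. Table 13 gives the counts.

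In each subsection the same percentage also appears as the incidence regarded as unacceptable and as the upper design proportion. No text ranks the sentence against the table, or says whether the percentage is a true or an observed rate.

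**The concern.** A monitoring board sees only observed counts. Taken at its word, a sentence that stops the study when the rate exceeds 22% can be applied only to the observed proportion. That is a different rule from Table 5. The table's boundary falls from 100% at 2 patients to 20.0% at 60, while the sentence is flat at 22%, so the two must cross.

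At stake is whether the same deaths, relapses or severe GVHD cases stop the trial or not. Also, the stopping probabilities and expected sample sizes in Tables 6, 8 and 14 describe the trial only if the count tables alone are followed.

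**Working it through.** **Inputs (all section 8.4).** Thresholds c: 22%, 19%, 36%. Expected rates: 15%, 12%, 26%. Unacceptable rates: 22%, 19%, 36%. Count boundaries: Tables 5, 7 and 13. Maximum 60 patients.

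**Step 1: reproduce the plan's figure.** Let f(n, x) be the probability of being unstopped after n patients with x events. Then f(n, x) = (1 − p)·f(n − 1, x) + p·f(n − 1, x − 1), and states that meet the rule are removed after each patient. Under continuous monitoring, the rule at n is to stop if x reaches the count for the next tabled n.

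- NRM at 22%: crossing 0.798, stopping before patient 60 0.790, expected N 29.7. The plan says "the probability of stopping the trial due to NRM if the level of toxicity is at high level of 22% is 0.79", and Table 6 gives 0.798, 0.790 and 29.7.
- Relapse at 19%: 0.799, expected N 29.8 (Table 8: 0.799, 29.8).
- GVHD at 36%: 0.790, expected N 31.8 (Table 14: 0.790, 31.8).

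The high-boundary columns therefore describe the printed counts and no other rule.

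**Step 2: compare the rules at each tabled look.** The smallest count exceeding c at n patients is floor(c·n) + 1. For NRM:

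| n | Table 5 count (rate) | Count exceeding 22% | Lower threshold |
|---|---|---|---|
| 2 | 2 (100%) | 1 | sentence |
| 7 | 3 (42.9%) | 2 | sentence |
| 12 | 4 (33.3%) | 3 | sentence |
| 18 | 5 (27.8%) | 4 | sentence |
| 24, 29, 35 | 6, 7, 8 (25.0%, 24.1%, 22.9%) | 6, 7, 8 | same |
| 41 | 9 (21.95%) | 10 | table |
| 47 | 10 (21.3%) | 11 | table |
| 54 | 11 (20.4%) | 12 | table |
| 60 | 12 (20.0%) | 14 | table |

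- Relapse: 1/3, 2/8 and 3/15 meet only the sentence. The rules agree at n = 22 and 29. 7/37, 8/44, 9/51, 10/59 and 11/60 meet only Table 7.
- GVHD: the sentence has the lower count at all eight looks from n = 3 to 24 (at n = 8, 3 against 5). The rules agree at 28, 31, 35 and 38. The table has the lower count at all seven looks from n = 42 to 60 (at n = 60, 21 against 22).

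**Step 3: probability of stopping by patient 60 at the expected rate.** This uses the same recursion, with the sentence applied as x/n > c on several schedules, because the plan gives none.

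| Rule | NRM 15% | Relapse 12% | GVHD 26% |
|---|---|---|---|
| Count table | 0.34 | 0.31 | 0.25 |
| Sentence, after every patient | 0.65 | 0.61 | 0.66 |
| Sentence, at the tabled looks | 0.54 | 0.49 | 0.54 |
| Sentence, ignoring the first 10 patients | 0.44 | 0.38 | 0.43 |
| Sentence, once at n = 60 | 0.058 | 0.051 | 0.045 |

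**Step 4: the same at the unacceptable rate (22%, 19%, 36%).** The count tables give 0.798, 0.799 and 0.790. The sentence gives 0.836, 0.823 and 0.866 at the tabled looks, but only 0.451, 0.473 and 0.506 if applied once at n = 60.

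**The case against.** The best reply is that section 8.4, read as a whole, shows what the percentages are. Each one reappears as the unacceptable incidence and as the upper proportion fed into the boundary calculation. The tables are worded as stopping counts, the text beneath restates those counts, and the operating characteristics reproduce from them alone. On this reading the percentage sentence is loose introductory wording and the table is the rule.

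Much of this stands, and it is probably what was intended. It does not remove the problem. The unacceptable-rate role already has its own sentence in each subsection, so the stop sentence reads as a further instruction. The tables are themselves introduced as guidelines, and the intolerance subsection manages with no percentage stop sentence. Monthly DSMB review could settle the reading, but it does not write it down.

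Three stronger inferences are not supported:

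- **That the plan's real chance of a false stop is 0.65, 0.61 and 0.66.** Those figures need the sentence applied from the first patient, so that one event in one patient stops the trial. The plan states no denominator, minimum number or look schedule, so no single figure follows from it.
- **That the sentence is always the stricter rule.** Late in the trial the tables are stricter, and one application at n = 60 stops far less often than the tables do.
- **That both conditions must hold together.** Nothing in the documents suggests a joint rule.

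**Conclusion.** The point holds as an unresolved contradiction in wording. For NRM, relapse and grade III-IV GVHD, section 8.4 contains two stop instructions and no order of precedence. If the percentages are read as observed rates, the instructions disagree early in one direction and late in the other. They agree at only 3 of 11 looks for NRM, 2 of 10 for relapse and 4 of 19 for GVHD.

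The size depends on the reading. At the expected rates the tables stop with probability 0.34, 0.31 and 0.25, and the sentence with anything from about 0.05 to 0.66. If the count tables are the sole rule, the printed stopping probabilities stand.

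The calculations assume independent patients with a constant event rate, outcomes known in enrolment order, and that the GVHD sentence means GVHD where it says NRM.

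**What to change.** Reconcile the passages so that each criterion has one governing stop rule, and say so explicitly. Of the two, only the count tables match the operating characteristics in Tables 6, 8 and 14. If they are kept, reword the three percentage sentences so that 22%, 19% and 36% are described only as the unacceptable true rates used to derive the boundaries, and correct the GVHD sentence to name GVHD. If an observed-rate rule is wanted instead, it needs a denominator, a look schedule and its own operating characteristics.

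Check the graft-failure subsection in the same way. Its sentence stops above 7.0%, which is the expected rate there, while the Table 9 boundaries run from 22.2% (2/9) down to 10.3% (6/58).

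If the tables are kept, the cost is wording only, with no new data or recalculation. The rewording leaves a separate problem open: the tables' own stopping probabilities at the expected rates (0.34, 0.31, 0.25) contradict the stated 1% type I error. Resolving that could change the boundaries themselves, so the two are best handled together.
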